5.2. Safety Analysis Sets

The SAF will consist of all randomized subjects except for the following subjects.

- Subjects who did not take the investigational product at all

- Subjects for whom absolutely no safety data are available following vaccination with the investigational product

6. HANDLING OF DATA

6.1. Handling of Missing Values

If a value cannot be measured or is the reference value because of, for example, the assessment was not performed, the test value was missing, or there was a problem with the test sample, this parameter will be handled as a missing value.

6.2. Allowable Assessment Time Point Deviation Window

For the tabulation at each time point of test and observation parameters, data meeting the allowable time window in days specified in “9.1 Test/Observation Schedule” of the study protocol will be used, and data will not be replaced using data from outside the allowable windows.

6.3. Handling of Antibody Titer Data Below the Limit of Quantitation

For the calculation of the descriptive statistics, if the measured antibody titer is below the limit of quantitation, then it will be treated as being the lower limit of quantitation divided by 2.

6.4. Handling of Adverse Event Data

6.4.1. Handling of Adverse Event Data When There Are Multiple Events In the Same Period

If the same PT occurs in the same subject occurs multiple times in the period in question (e.g., the safety assessment period or the specified period for each number of doses), then these will only be counted as a single event.

6.4.2. Handling Period of Adverse Event Data by Number of Injections

Adverse events to be summarized as the number of applicable vaccinations are those that occur after the vaccination on the day of the vaccination in question and before the vaccination on the day of the next vaccination. For the fourth vaccination, adverse events that occurred from the day of the fourth vaccination to the last day of the safety assessment period will be summarized.

7. STATISTICAL METHODS

7.1. General Methods

7.1.1. Significance Level and Confidence Coefficient

Since this study is an exploratory study, no significance levels have been established. The confidence intervals will be two-sided confidence intervals, and the confidence coefficient will be 95%.

7.1.2. Descriptive Statistics

Unless otherwise specified, the descriptive statistics shown in the following table will be calculated, depending on the type of the data.

Table 7.1.2: Descriptive Statistics

Data Category	Descriptive Statistics
Categorization/Sequential	Numbers and proportions of subjects
Continuous	Numbers of subjects, mean values, SDs, minimums, maximums, medians

7.1.3. Confidence Intervals (e.g., Seroprotection rate, Incidence)

When calculating the confidence intervals for the incidences of adverse events, etc., or the antibody seroprotection rates, Clopper & Pearson method will be used.

7.1.4. Number of Display Digits

The number of digits displayed will be as follows. Additionally, the digits after the number of display digits will be rounded off (or up), except for the minimum and maximum values.

Table 7.1.3: Number of Display Digits

Descriptive Statistics	Number of Display Digits
Number of subjects	Integers
Proportions	Values rounded off to 1 decimal place
Minimum and maximum values	Same as the number of digits of the original variable
Means, standard deviations, and medians	Number of digits of the original variable + 1

7.1.5. Display of Treatment Groups

The display of the treatment groups will be handled as shown in the following table.

Table 7.1.4: Treatment Groups

Treatment Groups	Display
BK1310 H group: Formulation H, 0.5 mL per dose	H group
BK1310 L group: Formulation L, 0.5 mL per dose	L group

7.1.6. Tabulation Time Points and Baselines

The tabulation time points will be displayed as shown in the table below. The baseline will be "Before

the first dose at Visit 1.”

Table 7.1.5: Tabulation Time Points

Notation for Tabulation		Assessment Time Points in the Protocol
Assessment Time Point	Abbreviation	
Before the first vaccination	V1	Before the first dose at Visit 1
4 weeks after the primary immunization	V4	Post-vaccination examination at Visit 4
Before the booster immunization	V5	Before the fourth dose at Visit 5
4 weeks after the booster immunization	V6	Postdose examination 2 at Visit 6 and at discontinuation

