### 12.2 Discontinuation Procedures

If a subject is discontinued from the study during the term of the study, the (sub)investigator will take whatever actions are appropriate for the subject, and will inform the monitor in question that the subject has been discontinued from the study.

The day of study discontinuation will be the day on which the (sub)investigator made the decision to discontinue the subject from the study.

The (sub)investigator will perform follow-up by examining the subject as much as possible to investigate the presence or absence of adverse events in the 2 weeks after vaccination with the investigational product (in the period up until the day of discontinuation if the day of discontinuation is more than 2 weeks after vaccination with the investigational product). If the subject is discontinued from the study after the third or fourth dose (except for subjects discontinued in the period from after Post-vaccination Examination 1 to before the fourth vaccination), blood samples for antibody titer measurement will be collected whenever possible 4 to 6 weeks after vaccination. If a subject has not completed all of the vaccinations, the subject's legal guardian will be given a full explanation of the vaccinations that the subject will receive after the subject has been discontinued from the study.

The concomitant medications will be confirmed at discontinuation, at the time of blood sample collection (except for Cohort 3), or at 2 weeks after vaccination, whichever comes last.

The (sub)investigator will record the day of discontinuation and the reason for discontinuation\* in the case report form.

For subjects for whom the specified observations/tests cannot be performed at discontinuation, or who did not come in for any study visits after discontinuation, the reasons for this, the subject's subsequent course, etc. will be followed up either in writing (correspondence) or by telephone or the like.

If the subject does not come in for a visit, the (sub)investigator or a clinical research coordinator will ask the subject's guardian to fill out the e-Diary as much as possible.

\*: The "reason for discontinuation" will be selected from among the following.

1. Adverse event
2. Death

3. Clearly unsuitable as a subject for the study
4. Study protocol deviation
5. Technical problem
6. Subject's legal guardian requested discontinuation

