2.4. Assessment Time Point

The Cohort 1 assessment time points are shown below.

Day of consent	Visit 1			Visit 2			Visit 3			Visit 4		Visit 5		Visit 6	
	1st vaccination			2nd vaccination			3rd vaccination			Post-vaccination Examination 1		4th vaccination		Post-vaccination Examination 2	
	Before	Vaccination	After	Before	Vaccination	After	Before	Vaccination	After	Before	After	Vaccination	Before	After	
Allowable window	D1			Visit 1 + 3 - 8 weeks			Visit 2 + 3 - 8 weeks			Visit 3 + 4 - 6 weeks		Visit 3 + 6 - 13 months		Visit 5 + 4 - 6 weeks	
Written informed consent	•														
Investigation of subject background		•										•			
Examination	•		• ^{*1}	•		• ^{*1}	•		• ^{*1}	•	•	•	• ^{*1}	•	•
Body temperature measurement (axillary)	•			•			•				•				
Investigational product vaccination			•			•			•			•			
Blood sampling (antibody titer)	•										•	•		•	• ^{*2}
Adverse events ^{*3}				•			•			•			•		
e-Diary ^{*4}															

*1: Subjects will be asked to wait in the hospital for 30 minutes after receiving the investigational product, and will be examined 30 minutes after vaccination.

*2: Blood samples will be collected for antibody titer measurement only at discontinuation after the third or fourth dose of the investigational product has been administered.

*3: An investigation will be performed to confirm whether or not the subject experienced any adverse events during the period from Visit 1 to Visit 4, and during the period from Visit 5 to Visit 6, based on examination of the subject at the study visits and based on the subject's e-Diary. Only serious adverse events will be investigated during the period from Visit 4 to Visit 5.

4: Every day until 14 days after each dose, if the subject's symptoms have not returned to normal by Day 14, then the subject will be asked to, as a rule, fill out the e-Diary until the symptoms return to normal.

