5.1. Efficacy Analysis Sets

The FAS will consist of all randomized subjects except for the following subjects.

- Subjects who did not take the investigational product at all
- Subjects for whom no antibody titer results at all could be obtained at 4 weeks after the primary immunization

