7.1.6. Tabulation Time Points and Baselines

The tabulation time points will be displayed as shown in the table below. The baseline will be “Before the first dose at Visit 1.”

Table 7.1.5: Tabulation Time Points

Notation for Tabulation		Assessment Time Points in the Protocol
Assessment Time Point	Abbreviation	
Before the first vaccination	V1	Before the first dose at Visit 1
4 weeks after the primary immunization	V4	Post-vaccination examination at Visit 4, and at discontinuation

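### Cohort 1 SAP Table 7.1.5 places discontinuation samples only in the post-booster row, so a valid post-dose-3 titer has no stated place in the primary endpoint

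*SAP*

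**What the plan says.** The Cohort 1 SAP, section 7.1.6, links each tabulation time point to protocol assessments in Table 7.1.5. V4, four weeks after the primary series, is linked to the Visit 4 examination and nothing else. V6, four weeks after the booster, is linked to "Postdose examination 2 at Visit 6 and at discontinuation".

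Footnote 2 to the schedule in section 2.4 of the same SAP says discontinuation blood is taken "only at discontinuation after the third or fourth dose of the investigational product has been administered". Protocol 12.2 sets the timing: "blood samples for antibody titer measurement will be collected whenever possible 4 to 6 weeks after vaccination". It also carves out one group: "except for subjects discontinued in the period from after Post-vaccination Examination 1 to before the fourth vaccination".

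SAP 6.2 limits tabulations to data inside the protocol's visit windows and adds that "data will not be replaced using data from outside the allowable windows". The Visit 6 window is "Visit 5 + 4 - 6 weeks"; the Visit 4 window is 4 to 6 weeks after Visit 3.

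SAP 5.1 removes from the FAS "Subjects for whom no antibody titer results at all could be obtained at 4 weeks after the primary immunization". Section 5 leaves detailed subject-handling rules to the sponsor, to be settled before database lock.

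In the Cohort 2 SAP, the V4 row of the corresponding table reads "Post-vaccination examination at Visit 4, and at discontinuation".

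**The concern.** In Cohort 1 a discontinuation sample can follow either dose 3 or dose 4, but Table 7.1.5 is written as if it could follow only dose 4. A titer drawn 4 to 6 weeks after dose 3 measures what the primary endpoint is meant to measure, and Protocol 12.2 has it collected at that time. If the table is applied as printed, the titer does not reach V4 and the infant leaves the denominator of the seroprotection rates for all eight antibodies listed in SAP 7.5.1. The infant might also be left out of the FAS, and the two cohorts would treat the same kind of sample differently for no stated reason.

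The choice should also not be left open. Protocol 5.2.1 unblinds the sponsor, monitors excepted, once the post-primary anti-PRP results are in. Membership of a denominator of 15 should therefore follow from a written rule rather than from a decision taken when the titer can be seen.

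**Working it through.** The plan gives no figure on this point to reproduce. The check is a comparison of passages, followed by a small calculation of what one infant is worth.

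**1. Who supplies a post-dose-3 discontinuation sample?** Protocol 12.2 requests blood after dose 3 or dose 4 but exempts infants who stop between Visit 4 and dose 4. Under that section the sample comes only from an infant who stopped after dose 3 and before Visit 4, and who therefore has no Visit 4 sample.

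**2. Does it fit V4?** On timing, yes: a draw 4 to 6 weeks after dose 3 meets the Visit 4 window. In Table 7.1.5, no: the V4 row names only the Visit 4 examination.

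**3. Does it fit V6?** In the table, it appears to, because V6 is the only row naming discontinuation. On timing, no: the window runs from Visit 5, which this infant never had, and SAP 6.2 accepts only in-window data.

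**4. Does another passage settle it?** No. SAP 7.5.4.2 only refers back to the missing-value rule, and that rule assigns no sample to a time point. SAP 6.2 could be read as admitting the sample to V4, but nothing says whether 6.2 or Table 7.1.5 prevails.

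**5. What does Cohort 2 do?** It assigns the sample to V4.

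**6. Size.** Inputs:
- 15 infants per group (Cohort 1 SAP 2.5).
- The denominator is infants with a titer result (SAP 4.2).
- Clopper-Pearson two-sided 95% limits (SAP 7.1.1 and 7.1.3).
- Assumption: one affected infant in a group. The documents give no dropout rate.

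For x responders among n, the lower limit is the 0.025 quantile of Beta(x, n − x + 1) and the upper limit is the 0.975 quantile of Beta(x + 1, n − x). When x = n the lower limit reduces to 0.025^(1/n), and the upper limit is 100%. For example, 0.025^(1/15) = 78.2% and 0.025^(1/14) = 76.8%.

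| Infant lost | Sample kept in V4 | Sample lost | Change in rate |
|---|---|---|---|
| Responder, no non-responders | 15/15 = 100% (78.2 to 100) | 14/14 = 100% (76.8 to 100) | 0 |
| Responder, one non-responder remains | 14/15 = 93.3% (68.1 to 99.8) | 13/14 = 92.9% (66.1 to 99.8) | −1/210 = −0.5 points |
| Non-responder, one other remains | 13/15 = 86.7% (59.5 to 98.3) | 13/14 = 92.9% (66.1 to 99.8) | +13/210 = +6.2 points |
| The only non-responder | 14/15 = 93.3% (68.1 to 99.8) | 14/14 = 100% (76.8 to 100) | +1/15 = +6.7 points |

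Each affected infant is 1/15 = 6.7% of a group.

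**The case against.** The best reply is that Table 7.1.5 only labels time points for display, and that SAP 6.2 decides which data enter a tabulation. A sample 4 to 6 weeks after dose 3 meets the Visit 4 window. The endpoint and the FAS are also worded by time since the primary series, not by visit label, so a sensible programmer could place the sample in V4. This has weight: it is why exclusion is probable rather than certain, and why 5.1 does not itself force the infant out of the FAS. It does not remove the conflict. The table is the only place in the SAP that assigns discontinuation samples to a tabulation time point, it points to V6, and no order of precedence is given.

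The second reply is that the matter may be empty. It needs an infant, among 30, who stops in a short interval and still returns for blood. Cohort 1 is exploratory, with no significance level, and the Cohort 2 initiation criterion does not refer to this table. The SAP also describes the redesign that followed Cohort 1's diphtheria results, so the sponsor may already have known whether such a sample existed; the documents do not say. All of this stands and limits the point to a minor one.

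Third, in both SAPs the discontinuation entry sits in the last row of the table, which suggests a drafting habit rather than a deliberate rule. That is plausible, but the printed mapping is the same whatever its origin.

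**Conclusion.** The concern holds as a minor error in the Cohort 1 SAP. As written, an in-window post-dose-3 discontinuation titer is pointed to a time point whose window it cannot meet and is not named under the one it fits. The likelier result is that it is discarded, not that it is counted as a post-booster value. Exclusion from the FAS is possible but not required by the wording.

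The numerical effect depends on how many infants stop between dose 3 and Visit 4, which is not given. With none, nothing changes. With one in a group of 15, the rate moves by 0 to 0.5 points in the examples where that infant is a responder, and by 6.2 to 6.7 points upward in those where the infant is a non-responder. The 6.7-point figure is an illustrative worst case for one infant, and all these shifts are small beside intervals more than 20 points wide. A sample outside the 4 to 6 week window would be excluded by SAP 6.2 in any case and is not part of this point.

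**What to change.** In Table 7.1.5 of the Cohort 1 SAP, split discontinuation samples by last dose received. Those taken after dose 3 from infants who stop before Visit 4 go to V4; those taken after dose 4 go to V6. Keep each subject to its own 4 to 6 week window under 6.2. Add a sentence to 5.1 stating that a discontinuation sample assigned to V4 counts as a post-primary titer for FAS entry.

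This brings the table into line with Protocol 12.2 and the Cohort 2 SAP and changes no study procedure. The cost is two table cells, one sentence and one line of derivation code.

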7.2. Subject Disposition

7.2.1. Analysis Population Eligibility

Analysis population(s): Randomized subjects

Analysis parameter: Eligibility for the FAS/safety analysis set (included, not included)

Analysis method: For each analysis parameter, the numbers and proportions of subjects will be calculated by group.

7.2.2. Disposition of Discontinued Subjects

Analysis population(s): Randomized subjects

Analysis parameter: Discontinued or completion after the vaccination of the investigational product, reason for discontinuation

Analysis method: For each group, the number and proportion of subjects discontinuing or completing will be calculated. Additionally, for subjects discontinuing, the numbers of subjects for each reason for discontinuation will be output.

Listings

Listing 7.2.2: Listing of Discontinuations

7.3. Demographic and Other Baseline Characteristics

Analysis population(s): FAS, safety analysis set

Analysis parameter: See Table 7.3

Analysis method: For each parameter, the number and proportion of subjects will be calculated, by group, for discrete data, and descriptive statistics will be calculated for continuous data. Additionally, if the FAS and the safety analysis set are the same, only the figures for the FAS will be output.

Table 7.3: Demographic and Other Baseline Characteristics/Analysis Parameters

Analysis Parameter		Data Category
Sex	Male, Female	Discrete
Age in months	≥ 2 and < 3 months, ≥ 3 months	Continuous
Concurrent illnesses	Yes, No	Discrete

Listings

Listing 7.3.1: Listing of Subject Backgrounds

Listing 7.3.2: Listing of Concomitant Medications

7.4. Status of Treatment Compliance

Analysis population(s): Safety analysis set

Analysis parameter: Presence or absence of receipt of a study drug injection

Analysis method: The number of subjects will be calculated for each number of injections (1, 2, 3, 4), by group.

Listings

Listing 7.3: Listing of Doses of Investigational Product

7.5. Efficacy Analyses

7.5.1. Primary endpoints

Analysis population(s): FAS

Analysis parameter: The anti-PRP antibody seroprotection (antibody titer ≥ 1 $\mu\text{g/mL}$) rate, and also the seroprotection rate for other antibodies (anti-diphtheria antibodies [REDACTED], anti-PT antibodies, anti-FHA antibodies, anti-tetanus antibodies, anti-poliovirus serotype 1 antibodies, anti-poliovirus serotype 2 antibodies, anti-poliovirus serotype 3 antibodies).

Analysis method: For each analysis parameter, the number of subjects, the number of subjects assessed for efficacy based on each antibody, the number of seroprotections, the seroprotection rate (%), and the two-sided, 95% confidence intervals will be calculated by group and time point (at 4 weeks after the primary immunization and at 4 weeks after the booster immunization).

7.5.2. Secondary endpoints

7.5.2.1 Anti-PRP Antibody Seroprotection (titer ≥ 0.15 $\mu\text{g/mL}$) Rate

Analysis population(s): FAS

Analysis method: Anti-PRP antibody seroprotection at (titer ≥ 0.15 $\mu\text{g/mL}$) rate

Analysis method: For each group, for each analysis parameter, the number of subjects, the number of subjects assessed for efficacy, the number of seroprotections, the seroprotection rate (%), and the two-sided 95% confidence intervals will be calculated by time point (at 4 weeks after the primary

immunization and at 4 weeks after the booster immunization).

7.5.2.2 Antibody Titer Profiles

Analysis population(s): FAS

Analysis parameter: Titers of each type of antibody (anti-PRP antibodies, anti-diphtheria antibodies [REDACTED] [REDACTED], anti-PT antibodies, anti-FHA antibodies, anti-tetanus antibodies, anti-poliovirus serotype 1 antibodies, anti-poliovirus serotype 2 antibodies, anti-poliovirus serotype 3 antibodies)

Analysis method: For each group, for each analysis parameter, the number of subjects, the number of subjects assessed for efficacy, the geometric mean, the geometric standard deviation, the two-sided 95% confidence interval of the geometric mean, and the minimum, median, and maximum values will be calculated.

Listings

Listing 7.5.2.2: Antibody Titer Listing

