## (4) Plans for This Study

The introduction of a DPT-IPV-Hib pentavalent vaccine would make it possible to simultaneously, in one product, confer basic immunity against pertussis, diphtheria, tetanus, polio, and Hib. This would be advantageous from the standpoint of alleviating the burden placed on infants by injections as well as reducing the burden associated with drug management. The purpose of this study is to develop BK1310, which is a pentavalent vaccine that combines MT-2301, which is an influenza b conjugate vaccine that is being developed in Japan, with TETRABIK, which is a DPT-IPV combined vaccine. This study has been designed to confirm safety and immunogenicity against Hib antigen in Cohort 1 in order to confirm the safety and efficacy of BK1310 in the clinical setting. The subsequent cohort, Cohort 2, has been designed to verify the noninferiority of BK1310 to the control, which is simultaneous vaccination with ActHIB® and TETRABIK.

Based on an investigation that took into account the results that had been obtained for the anti-diphtheria antibody titer in Cohort 1, the design was subsequently changed so that Cohort 2 would be an exploratory study in which simultaneous vaccination with ActHIB® and TETRABIK in the primary immunization is used as the control. Additionally, Cohort 3 was established so that the (sub)investigator could measure the antibody titer following the booster immunization in subjects completing Cohort 2, depending on the results obtained after the primary immunization in Cohort 2, or the subject's (legal guardian's) request.

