Because there is no experience with the use of BK1310 in infants, this design was selected in order to confirm, on an exploratory basis, the safety and immunogenicity against the Hib antigen of BK1310 before advancing to Cohort 2, in which a large number of subjects will receive a vaccination with the investigational product. As far as the Hib antigen level of the investigational product is concerned, because the results of the Japanese phase 2 clinical study of MT-2301 revealed that efficacy and safety were comparable to those achieved with ActHIB®, both in the 5 µg group and in the 10 µg group, 2 dose levels, 5 µg (the L group) and 10 µg (the H group), as the level of polysaccharide, were selected for the level of Hib antigen of the investigational product for use in Cohort 1 as well. Additionally, for Cohort 2, in order to verify noninferiority with respect to simultaneous immunization with ActHIB® and TETRABIK in the antibody seroprotection rate following vaccination with 3 doses of BK1310 against each of the antigens contained in BK1310, the study was initiated as an active-controlled, parallel-group, multicenter study. Subsequently, the decision was made to change the study from being a confirmatory study, its initial design, to being an exploratory study with a group that would receive a vaccination simultaneously with ActHIB® and TETRABIK as a control, because of the results that were obtained in Cohort 1 for the anti-diphtheria antibody titer after the primary immunization. Furthermore, it was decided that the exploratory comparison versus the control in Cohort 2 would be performed up until Visit 4 because it was thought that this could be done using an investigation based on the primary immunization. In addition, because Cohort 2 was changed to a design that included the period up until after the primary immunization, Cohort 3 was established so that the (sub)investigators could measure the antibody titer following the booster immunization in subjects who had completed Cohort 2, depending on the results obtained after the end of the primary immunization or the wishes of the subject (subject's legal guardian). For the Hib antigen levels of the investigational product, the results of Cohort 1, among other findings, will be judged comprehensively, and 1 dose, either the L group dose or the H group dose, will be selected and used.

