#### (2) Secondary Endpoints

##### 1) Cohort 1 and Cohort 2

- The anti-PRP antibody seroprotection (antibody titer  $\geq 0.15 \mu\text{g/mL}$ ) rate and the geometric mean antibody titer for anti-PRP antibodies at 4 weeks after the primary immunization
- The geometric mean antibody titers for pertussis, diphtheria toxin, tetanus toxin, and attenuated poliovirus at 4 weeks after the primary immunization

##### 2) Cohort 1

- The anti-PRP antibody seroprotection (antibody titer  $\geq 1 \mu\text{g/mL}$ ) rate, the anti-PRP antibody seroprotection (antibody titer  $\geq 0.15 \mu\text{g/mL}$ ) rate and the geometric mean antibody titer for anti-PRP antibodies at 4 weeks after the booster immunization.

- (b) The antibody seroprotection rates and geometric mean antibody titers for pertussis, diphtheria toxin, tetanus toxin, and attenuated poliovirus at 4 weeks after the booster immunization

*Rationale*

- (1) The assessment was planned to be performed based on an immunological endpoint, in accordance with the “Guidelines for Clinical Studies of Vaccines to Prevent Infectious Diseases” (PFSB/ELD Notification No. 0527-5, issued May 27, 2010). With Hib, it is generally held that an anti-PRP antibody concentration of 1 µg/mL is needed for long-term infection prevention, and the anti-PRP antibody seroprotection rate at an Hib level of at least 1 µg/mL in the primary immunization was therefore established as the primary endpoint. The assessment was planned to be performed based on immunological endpoints for pertussis, diphtheria toxin, tetanus toxin, and attenuated poliovirus, as well, in order to confirm the effects of the addition of the Hib antigen on the efficacy of DTP-IPV.
- (2) 1) (a) The anti-PRP antibody seroprotection rate at an Hib level of at least 0.5 µg/mL, the level that is considered necessary for preventing Hib infection in the primary immunization, and the geometric mean antibody titer at an Hib antigen level of at least 0.15 µg/mL, were established as secondary endpoints.
  - 1) (b) The geometric mean antibody titers for pertussis, diphtheria toxin, tetanus toxin, and poliovirus in the primary immunization were established as secondary endpoints.
  - 2) (a) Long-term infection prevention through the booster immunization, and the anti-PRP antibody seroprotection rate and geometric mean antibody titer required to prevent infection, were established as secondary endpoints.

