## 7. Investigational Product

### 7.1 Names of the Investigational Products

#### (1) Investigational Drug

Name: BK1310, H and L formulations

Expected nonproprietary name: Adsorbed-purified pertussis/diphtheria/tetanus/inactivated polio (Sabin strain)/Haemophilus b (non-toxic mutant diphtheria toxin conjugate) combination vaccine

The H and L formulations are syringe formulations that contain, in 0.5 mL, 10 µg and 5 µg, respectively, of Hib antigen, in terms of the quantity of oligosaccharide, and that also contain the same antigen levels as those contained in TETRABIK.

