2.3. Randomization Method

In this study, subjects will be randomly assigned to either the BK1310:H group or the BK1310:L group using a variable block method.

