2.5. Sample Size Justification

○ Target sample size

Cohort 1: 30 subjects (BK1310 L group: 15 subjects; BK1310 H group: 15 subjects)

Rationale

In Cohort 1, the sample size was set at 15 subjects per group, 30 subjects in total, as the number of subjects that will make it possible to confirm that the anti-PRP antibody concentrations and antibody

seroprotection rate have not decreased appreciably, in order to confirm that combining the vaccines does not result in a reduction in Hib antigen immunogenicity.

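### Cohort 1 randomises formulation H against L and helps decide which goes forward, yet its SAP plans no H-versus-L estimate; a descriptive ratio and rate difference with 95% intervals should be added

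*SAP*

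**What the plan says.** The SAP document holds two plans, one for Cohort 1 and one for Cohort 2.

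**Cohort 1 design.** Under Cohort 1 SAP 2.3, "subjects will be randomly assigned to either the BK1310:H group or the BK1310:L group using a variable block method". Section 2.5 gives the size as "Cohort 1: 30 subjects (BK1310 L group: 15 subjects; BK1310 H group: 15 subjects"). Protocol 7.1 states that H and L hold 10 µg and 5 µg of Hib antigen per 0.5 mL and "that also contain the same antigen levels as those contained in TETRABIK".

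**Cohort 1 analyses.** Section 7.5.1 covers the seroprotection rates, for which "the two-sided, 95% confidence intervals will be calculated by group and time point". Section 7.5.2.1 does the same for the 0.15 µg/mL anti-PRP threshold. Section 7.5.2.2 covers titers: "For each group, for each analysis parameter, the number of subjects, the number of subjects assessed for efficacy, the geometric mean", then the geometric SD, the interval for the geometric mean, and order statistics. Section 7.5.3, added for a further diphtheria measurement, follows the same per-group pattern. The blacked-out text in these sections lies in titles and parameter names. The method paragraphs are readable, and none contains a between-group quantity.

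**Cohort 2 analyses.** Cohort 2 SAP 7.5.1 and 7.5.2.1 plan a Farrington-Manning 95% interval for the H-minus-control rate difference. Section 7.5.2.2 plans a 95% interval for the H/control ratio of geometric means. Like Cohort 1, Cohort 2 has no significance level.

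**Use of Cohort 1.** Protocol 5.2.1 (Rationale) says that the Cohort 1 results, with other evidence, "will be judged comprehensively, and 1 dose, either the L group dose or the H group dose, will be selected and used". Protocol 1(4) says that Cohort 2 was redesigned as exploratory after considering "the results that had been obtained for the anti-diphtheria antibody titer in Cohort 1".

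**The concern.** H versus L is the only randomised comparison in Cohort 1, and the only one in the trial in which just the amount of Hib conjugate differs. In Cohort 2 the control infants also receive Hib, on a tetanus toxoid carrier and at a separate site, so that cohort cannot isolate the effect of amount.

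A plan that randomises two formulations, and draws on the result to choose one, would normally state the difference between them with its uncertainty. This plan leaves the reader two intervals from 15 infants each. Overlap of such intervals is easily taken to mean no difference, when the data may be compatible with a sizeable one. What is at stake is how clearly the evidence for the chosen formulation can be stated, for anti-PRP and for the diphtheria response that led to the redesign.

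**Working it through.** **The plan's own figure.** 15 + 15 = 30 agrees with the stated Cohort 1 total. The size cannot be derived further, because Protocol 6.1 and Cohort 1 SAP 2.5 give no rate, SD, margin or power.

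**Inputs.** n = 15 per group and two-sided 95% intervals come from the documents. The SD of log10 titer does not appear in them. It is assumed to be 0.5, with a range of 0.4 to 0.7, and equal in the two groups. Critical values are t(0.975, 14) = 2.145 and t(0.975, 28) = 2.048.

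**Titers.**

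- Half-width of one group's interval on the log10 scale: h1 = 2.145 × SD / √15. At SD 0.5 this is 0.277, a factor of 10^0.277 = 1.89.
- Two such intervals stop overlapping when the difference in mean log10 titers exceeds 2 × h1. At SD 0.5: 0.554, so 10^0.554 = 3.58-fold.
- Half-width of the interval for the H/L ratio: h2 = 2.048 × SD × √(2/15). At SD 0.5: 0.374, so 10^0.374 = 2.37-fold. The ratio interval excludes 1 beyond that.

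| Assumed log10 SD | Observed ratio at which separate intervals stop overlapping | Observed ratio at which the ratio interval excludes 1 |
|---|---|---|
| 0.4 | 2.77 | 1.99 |
| 0.5 | 3.58 | 2.37 |
| 0.7 | 5.96 | 3.34 |

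The relation between the two columns does not depend on the SD. Non-overlap corresponds to |t| = 2 × 2.145 / √2 = 3.03 on 28 degrees of freedom, a two-sided p of about 0.005.

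As an illustration, suppose the true H/L ratio is 2.5 (also an assumption). By the noncentral t distribution, the ratio interval excludes 1 in 56% of trials (75% at SD 0.4, 32% at SD 0.7). By simulation, the separate intervals fail to overlap in 23% (41% and 9%).

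**Seroprotection rates.** The planned Clopper-Pearson interval for 15/15 has lower limit 0.025^(1/15) = 78.2%. For 14/15 the interval is 68.1% to 99.8%, and for 12/15 it is 51.9% to 95.7%. The corresponding score-type intervals for the difference are:

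| Group counts | Difference (points) | 95% interval |
|---|---|---|
| 15/15 v 15/15 | 0 | -20.4 to 20.4 |
| 15/15 v 14/15 | 6.7 | -14.4 to 29.8 |
| 15/15 v 12/15 | 20.0 | -2.4 to 45.2 |
| 15/15 v 11/15 | 26.7 | 3.6 to 51.9 |

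The first row has a closed form: 1.96² / (15 + 1.96²) = 3.84 / 18.84 = 20.4 points either side of zero.

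**The case against.** **The dose choice is not shown to rest on interval overlap.** A reader might infer that it does. Protocol 5.2.1 bases the choice on Cohort 1 together with other evidence. Protocol 5.2.2 sets a safety criterion and a count criterion (fewer than 2 subjects below 1 µg/mL anti-PRP), and leaves further detail to separate procedures. This stands. Those criteria are absolute, however, and both formulations could meet them, so they do not show how H and L compare.

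**H versus L is not a stated question.** A reader might take the endpoint rationale in Protocol 5.4.1, "in order to confirm the effects of the addition of the Hib antigen on the efficacy of DTP-IPV", as setting one. It concerns adding Hib to the four-component vaccine. H and L both contain Hib, so their contrast addresses amount only, and no document names an H-versus-L diphtheria effect as an objective. Protocol 13.3.2.1 asks for differences only against control, so the Cohort 1 SAP breaches nothing. This stands.

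**The timing limits the benefit.** The Cohort 2 SAP (2.3 and Table 7.1.4) already names H. The decision to start Cohort 2 follows the primary immunization, so contrasts at V5 and V6 could not have informed it. The Cohort 1 SAP also already describes the exploratory design, which the protocol attributes to Cohort 1 results. The addition would therefore be a retrospective summary.

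**Little information is lost.** The ratio and its interval can be computed from each group's n, geometric mean and geometric SD, and the rate difference from the counts. This is true, so the gap is one of presentation. It also means that closing it costs almost nothing.

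**Imprecision and multiplicity.** With SD 0.5, 80% power for a 2-fold ratio would need about 44 per arm. Eight antibodies at three visits give 24 ratios, of which 24 × 0.05 = 1.2 would be expected to exclude 1 by chance if H and L were identical. Both points call for a descriptive label. Neither supports omission: the Cohort 1 SAP cites small numbers for dropping its multicenter and subgroup analyses (7.5.4.4, 7.6.1.4) but gives no reason here.

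**Conclusion.** The concern holds in a limited form. The Cohort 1 SAP plans no between-group estimate for the one comparison that Cohort 1 randomises, while the Cohort 2 SAP plans such estimates under the same exploratory status. If the formulations are compared by eye from the planned output, separate intervals need about a 3.6-fold observed difference in geometric means before they part (2.8 to 6.0). The ratio interval excludes 1 at about 2.4-fold (2.0 to 3.3). These figures rest on 15 evaluable infants per group and an assumed common log10 SD of 0.5 (0.4 to 0.7).

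The documents do not support concluding that the Cohort 2 dose was chosen on overlapping intervals, or that a planned diphtheria question goes unanswered. Adding the contrast would give a correct interval, but not a precise one.

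**What to change.** In the Cohort 1 SAP:

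- **7.5.2.2 and 7.5.3.2:** add the H/L ratio of geometric mean titers with a two-sided 95% interval, from the difference in mean log titers.
- **7.5.1, 7.5.2.1 and 7.5.3.1:** add the H-minus-L difference in seroprotection rate with a Farrington-Manning 95% interval, as in Cohort 2.
- **Labelling:** put the emphasis on anti-PRP and anti-diphtheria at V4. State that all contrasts are descriptive, unadjusted for multiplicity, and carry no test or decision rule.
- **Reporting:** present them as supporting evidence for the formulation carried to the confirmatory study, not as a prespecified basis for the Cohort 2 dose.

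The cost is a few sentences and extra columns in existing tables, with no new data. The downside is visibly wide intervals: about -20 to +20 points when both groups are 15/15, and a factor of about 2.4 either way on the titer ratio at SD 0.5.
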